5.2.6 Follow-up

AIO-Studien-gGmbH

After discontinuation of treatment, all patients will be followed-up for survival every 3 months. First visit of the follow-up period will take place 3 months after EOT visit. Follow-up of the individual patient will continue until death or until study is terminated. The following information will be collected during the follow-up:

- Survival data
- Subsequent anti-cancer therapy
- Study drug related adverse events continuing from treatment phase will be followed-up until the event has resolved or stabilized

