7.5 Safety recording and reporting requirements

7.5.1 Recording periods

- Adverse events are recorded from time of signed informed consent until 6 weeks (EoT visit) after surgery.
- Serious adverse events are recorded from time of signed informed consent until 90 days after last dose of IMP or for 6 weeks after surgery if the subject initiated new anticancer therapy (e.g. radio-chemotherapy)
- Pregnancies occurring in a study subject are recorded from time of signed informed consent until 120 days after last dose of IMP.

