7.6 Handling of Safety Parameters

7.6.1 Adverse events

Adverse events can be spontaneously reported or elicited during open-ended questioning, examination, or evaluation of a subject. (In order to prevent reporting bias, subjects should not be questioned regarding the specific occurrence of one or more AEs.)

Medically significant adverse events regardless of causality will be followed until resolved or considered stable. All subjects with serious adverse events must be followed up for outcome.

It will be left to the investigator's clinical judgment to determine whether an adverse event is related and of sufficient severity to require the subject's removal from treatment or from the study. A subject may also voluntarily withdraw from treatment due to what he or she perceives as an intolerable adverse event. If either of these situations arises, the subject should be strongly encouraged to undergo an end-oftreatment assessment and be under medical supervision until symptoms cease or the condition becomes stable.

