8.4.4 Safety evaluation

Adverse events:

All information recorded such as onset date, stop date, duration, maximum intensity, seriousness, relationship to study drug and outcome will be listed.

Summary tables will be presented. These tables provide the number and percentage of patients with adverse events. Associated adverse event tables present the total number of patients reporting at least one specific event and the maximum toxicity grade. Thus, patients reporting more than one episode of the same event are counted only once by the worst grade per patient.

Tabulations consist of the number and percentages of patients involved per CTC category and CTC term, the highest relation to study drug, and the maximum severity. Special tables will be displayed for CTC grade III / IV adverse events and for adverse events resulting in discontinuation of the trial. Additionally, analysis will be restricted to adverse events judged to be at least possibly related to study drug.

Laboratory parameters:

Abnormal laboratory parameters will be tabulated according to incidence and severity according to NCI CTCAE V4.03 and analyzed descriptively.

9 Independent Data Monitoring Committee

An Independent Data Monitoring Committee (IDMC) has been convened to assess the safety data, and provide recommendations to the Sponsor and Coordinating Investigator upon the stop or continuation of the study. The members of the IDMC serve in their individual capacity and provide their expertise and recommendations. The IDMC will review cumulative study data to evaluate subject safety, conduct an interim analysis and reassess the risk/benefit of the study.

The role and responsibilities of the IDMC are described in detail in a separate IDMC Charter.

10 Data Quality Assurance

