2. GENERAL CONSIDERATIONS

2.1 Conduct of Analysis

Two analyses will be performed for this study.

- Main analysis will be performed after all patients had their end of treatment, data entry for all visits except the follow-up visits is complete, data were cleaned, a Data Review Meeting was performed and database snapshot has been completed.
- Addendum analysis will be performed after last patient completed the entire study, follow-up data entry and cleaning are complete and database was closed.

Main analysis will summarize all data recorded up to the time of the database snapshot. Addendum analysis will only present data captured during follow-up. This means, the addendum analysis may only include overall survival, end of study details and subsequent cancer therapy. An SAE listing will also be prepared to show possible follow-up information of SAEs ongoing after end of treatment.

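### SAP 2.1 does not ensure that the main-analysis snapshot falls after every patient's SAE window has closed, and the addendum makes no provision for later-onset SAEs or updated non-serious AEs

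*Protocol*

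**What the plan says.** **Recording windows (Protocol 7.5.1).** For all AEs: "Adverse events are recorded from time of signed informed consent until 6 weeks (EoT visit) after surgery". For SAEs: "Serious adverse events are recorded from time of signed informed consent until 90 days after last dose of IMP". With the clause that follows, the SAE window runs "until 90 days after last dose of IMP or for 6 weeks after surgery if the subject initiated new anticancer therapy".

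**Follow-up of events already open.** Protocol 5.2.6: "Study drug related adverse events continuing from treatment phase will be followed-up until the event has resolved or stabilized". Protocol 7.6.1: "Medically significant adverse events regardless of causality will be followed until resolved or considered stable". Protocol 7.6.3 also asks for follow-up of AEs until return to baseline or stabilisation. Footnote 7 of the schedule of assessments, attached to the adverse-event entry in the follow-up column, mentions only ongoing SAEs.

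**Reporting promised (Protocol 8.4.4).** "All information recorded such as onset date, stop date, duration, maximum intensity, seriousness, relationship to study drug and outcome will be listed". Section 8.4.1 also calls for summary tables of SAEs.

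**Timing of the analyses (SAP 2.1).** "Main analysis will be performed after all patients had their end of treatment, data entry for all visits except the follow-up visits is complete". Cleaning, a data review meeting and the snapshot come next, and the main analysis covers whatever is in the database at that snapshot. The addendum is confined to follow-up data: overall survival, end-of-study information and later cancer therapy. Its one safety output is described thus: "An SAE listing will also be prepared to show possible follow-up information of SAEs ongoing after end of treatment". The AE and SAE tables (14.4.1-14.4.4) are not scheduled for a second run.

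**The concern.** The main analysis is triggered by the last EOT, but the protocol's SAE window normally closes later. Neither document gives a minimum interval between the last EOT and the snapshot, or says where an SAE starting after the snapshot would be reported. Data from the follow-up phase are exempt from the entry condition that triggers the main analysis, and that is the phase in which the schedule places the 90-day SAE rule.

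Frequency and severity of AEs is a primary endpoint. Protocol 6.3.1 itself warns that immune-related events can appear months after the last dose. If the snapshot comes early, patients enrolled first are observed for their full SAE window and the last ones may not be. An AE that is still open at EOT and later worsens, becomes serious or fails to resolve would keep its old grade, seriousness and outcome in every planned output, unless it was already an SAE. Reversibility of such events is part of judging a treatment given before curative surgery. SAP 2.14, which lists departures from the protocol, does not mention this narrowing.

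**Working it through.** The plan gives no figure for the interval between EOT and the close of the SAE window. Its only safety-related design figure is that events with incidence above 9.5% are seen at least once with 95% probability at N=30. This reproduces (1 - 0.05^(1/30) = 0.0950) and plays no part below.

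**Inputs.** Dose 2 on Day 21 +/- 3, discharge on Day 60-74 and pre-surgery visit on Day 43-50 (schedule). EOT 6 weeks after surgery, about 4 weeks after discharge, or within 28 days of early discontinuation (Protocol 3.2). SAE window of 90 days (7.5.1). 30 patients (3.5) over about 36 months (3.7).

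**Step 1: on schedule, no new therapy.** Window closes = dose-2 day + 90. EOT = discharge + 28, so Day 88 to Day 102. Gap = window close - EOT.

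| Dose 2 | Window closes | Gap if EOT is Day 88 | Gap if EOT is Day 102 |
|---|---|---|---|
| Day 18 | Day 108 | 20 days | 6 days |
| Day 21 | Day 111 | 23 days | 9 days |
| Day 24 | Day 114 | 26 days | 12 days |

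The gap is 6-26 days. As a cross-check, suppose surgery takes place on the pre-surgery visit day. EOT is then Day 43-50 + 42 = Day 85-92, and the gap is 108 - 92 = 16 to 114 - 85 = 29 days.

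**Step 2: new anticancer therapy started after surgery.** The window then ends 6 weeks after surgery, which is EOT. The gap is 0.

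**Step 3: early discontinuation.** One dose on Day 1: the window closes on Day 91. If treatment is discontinued on Day 1, EOT is by Day 29 and the gap is at least 62 days. If discontinued on Day 21, EOT is by Day 49 and the gap is at least 42 days. If discontinued directly after dose 2, the gap is at least 90 - 28 = 62 days. The 6-week clause counts from surgery, so how it applies to a patient who is never operated on is not stated.

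**Step 4: patients exposed.** With even accrual, 30 / (36 x 30.44 days) = 0.0274 patients per day. Over 6-26 days this adds 0.16-0.71 patients to the last one; over 62 days it adds 1.70. These are upper bounds, because the time for entry, cleaning and data review is not deducted.

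**Step 5: effect of one missed patient with an SAE.** 1/30 = 3.3 percentage points. With the Wilson intervals of SAP 6.2.3:

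| SAE patients | Rate | 95% CI |
|---|---|---|
| 3/30 | 10.0% | 3.5-25.6 |
| 4/30 | 13.3% | 5.3-29.7 |
| 11/30 | 36.7% | 21.9-54.5 |
| 12/30 | 40.0% | 24.6-57.7 |

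The counts are illustrative, near the 10% and 37.2% reference rates in Protocol Table 3.

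**Step 6: what the addendum covers.**

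| Information arising after the snapshot | Planned output |
|---|---|
| Follow-up of an SAE ongoing after EOT | Addendum SAE listing |
| SAE with onset after the snapshot | None described |
| Non-serious AE that worsens or becomes serious | None described |
| Stop date and outcome of a non-serious AE | None described |

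**The case against.** A reader might infer that the AE tables are cut at the last EOT visit, so that later SAEs and AE outcomes in the last patients certainly reach no table. The documents do not support this, for four reasons.

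- The cut is the snapshot. It follows data entry, cleaning and a data review meeting, which may take as long as the 6-26 day gap. SAEs must also reach the safety desk within 24 hours (Protocol 7.5.2), so many late SAEs would be known by then. This stands, but only as a likelihood: the snapshot date is open, and 7.5.2 sets no time limit for eCRF entry.
- The new-therapy clause closes the gap for operated patients who start such therapy, and Protocol section 3 leaves later treatment to local standards. This stands for those patients.
- AE outcome is in no SAP table for any patient, because Protocol 8.4.4 plans it as a listing. So no outcome table is lost, only late updates to Listing 16.2.4.2. Maximum severity and seriousness are tabulated, however, so a late change in either would affect Tables 14.4.1-14.4.4.
- The SAP wording on the addendum listing states a purpose and sets no explicit filter on onset date, and Listing 16.2.4.5 has no onset limit. A generous programmer could include new SAEs. The text does not require it.

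It can also be said that non-serious AEs are recorded only to EOT and that footnote 7 limits later follow-up to SAEs. Protocol 5.2.6, 7.6.1 and 7.6.3 go further, so the protocol is not consistent with itself here.

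Finally, the size is small. If each exposed patient had a 5-10% chance of a new SAE in the gap (an assumption; the documents give no figure), the expected number missed is 1.16 x 0.05 = 0.06 to 1.71 x 0.10 = 0.17, before allowing for cleaning time. The trial is descriptive, and the Wilson intervals near the 37.2% reference rate are about 33 points wide.

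**Conclusion.** The point holds as a gap in SAP 2.1. Nothing places the snapshot after the protocol's SAE window has closed in every treated patient, and the addendum as worded provides neither for SAEs starting after the snapshot nor for updated grade, seriousness, stop date and outcome of non-serious AEs. Loss of late SAEs is possible but not certain.

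The window outlasts EOT by about 6-26 days on schedule, by at least 42-62 days after a single dose, and by nothing where new therapy starts after surgery by EOT. About the last one or two patients are exposed to a missed new-onset SAE, at 3.3 points of the SAE rate each. The AE-update part does not depend on how long cleaning takes, since such updates can arrive at any time during follow-up.

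Assumptions: EOT is 28 days after discharge, accrual is even over 36 months, and the snapshot is taken close to the last EOT. A later snapshot reduces the exposure. This is a cheap improvement to the reporting of a primary endpoint and no threat to the trial's conclusions.

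**What to change.** 1. **SAP 2.1, main analysis.** Take the snapshot no earlier than the later of the last EOT and the close of the 7.5.1 SAE window in every treated patient. This alone settles new-onset SAEs within the window.
2. **SAP 2.1, addendum.** Replace the listing of ongoing SAEs by updated Listings 16.2.4.2 and 16.2.4.5 covering all AEs and SAEs, including new-onset SAEs and AEs still open at EOT. Re-run Tables 14.4.1-14.4.4 if any grade, seriousness status or count has changed since the snapshot.
3. **Protocol.** Reconcile schedule footnote 7 with sections 5.2.6, 7.6.1 and 7.6.3 on which events are followed after EOT.

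Cost: SAP wording, a small amount of re-programming on existing programs, and no data beyond what the protocol already asks for. On schedule the main analysis moves by at most a few weeks (up to 26 days, or 29 under the cross-check), less whatever cleaning already takes. The wait after EOT is longer only if one of the last patients stops early.

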7.5.2 Recording and Reporting requirements

Adverse events in general: All adverse events are documented by the participating site in the patient's medical records and the eCRF. The investigator is responsible for ensuring that all adverse events observed by the investigator or reported by patients are properly captured in the patient's medical records (source data).

The following adverse event attributes must be assigned by the investigator:

- adverse event diagnosis or syndrome(s) (if known, signs or symptoms if not known),
- event description (with detail appropriate to the event),
- dates of onset and resolution,
- seriousness (yes / no),
- severity (according to NCI CTCAE V4.03),
- assessment of relatedness to study treatment (see section 7.3),
- outcome:
 - recovered / resolved
 - recovered / resolved with sequelae

- o not recovered / not resolved
- o deteriorating/worsening
- o fatal
- o unknown (only applicable if patient is lost to follow-up); and
- action taken:
 - o **none**
 - dose reduced (new dose)
 - o study drug temporarily interrupted
 - o study drug permanently discontinued (stop date)
 - o not applicable
 - o **unknown**

Serious adverse events:

- For each patient any adverse event or abnormal laboratory test value that is serious occurring during the course of the study must be reported immediately (within 24 hours / GCP-V § 12(4)) after awareness to the safety desk (contact details are provided in the Investigator Site File) utilizing a completed SAE Report Form.
- Serious Adverse Events that are unexpected and considered related to IMP and occur after the completion of the trial should be reported to the sponsor (AIO-Studien-gGmbH) within one working day [ICH E2A III.E.3].

Events of clinical interest: Selected non-serious and serious adverse events that are also known as Events of Clinical Interest (ECI) are subject to expedited reporting by the investigator.

For the time period beginning when the consent form is signed (registration) until start of treatment, any ECI, or follow up to an ECI, that occurs to any subject must be reported within 24 hours of investigators awareness to the safety desk if it causes the subject to be excluded from the trial, or is the result of a protocol-

specified intervention, including but not limited to washout or discontinuation of usual therapy, diet, placebo treatment or a procedure.

 For the time period beginning at start of treatment through 6 weeks following surgery, any ECI, or follow up to an ECI, whether or not related to IMPs, must be reported within 24 hours of investigators awareness to safety desk.

Other reportable events: For each patient any 'other reportable' event occurring until 6 weeks after surgery must be reported immediately (within 24 hours) after investigator's awareness to the safety desk.

Pregnancy: Pregnancies occurring during study treatment and up to 120 days after last dose must be reported by the investigator on the **Pregnancy Report Form** within 24 hours after awareness to the safety desk.

Follow up case reports have to be provided as new information becomes available. If an SAE is experienced in addition to or related to the pregnancy e.g. an induced or spontaneous abortion, also an SAE Report has to be sent to the safety desk within 24 hours / GCP-V § 12(4) after first knowledge.

Overdose: If an adverse event(s) is associated with ("results from") the overdose of IMP, the adverse event(s) is reported as a **serious adverse event**, even if no other seriousness criteria are met. An SAE Report has to be sent to the safety desk within 24 hours of investigators awareness.

If an overdose is administered without any associated clinical symptoms or abnormal laboratory results, the overdose is reported as a **non-serious Event of Clinical Interest** (ECI), using the terminology "accidental or intentional overdose without adverse effect." An SAE Report has to be sent to the safety desk within 24 hours of investigators awareness.

Abnormal Laboratory results: Abnormal laboratory test results will be recorded on the laboratory results pages of the eCRF. Laboratory-test-value abnormalities should additionally be considered an AE in case they are:

- 1. Accompanied by clinical symptoms
- 2. Leading to a change in study medication (e.g. dose modification, interruption or permanent discontinuation)
- 3. Requiring a change in concomitant therapy (e.g. addition of, interruption of, discontinuation of, or any other change in a concomitant medication, therapy or treatment)

In general it is the investigator's responsibility to review all abnormal laboratory results and to determine if a given value represents a clinically significant change compared to previously obtained values and results in an Adverse Event or not.

Any laboratory result abnormality fulfilling the criteria for a serious adverse event (SAE) should be reported as such, in addition to being recorded as an adverse event in the eCRF.

7.5.3 Sponsor obligations

The Sponsor will ensure compliance with all regulatory reporting requirements including the notification of the appropriate Ethics Committees, Competent Authority of all serious adverse events occurring at the site in accordance with national law, ICH Good Clinical Practice and European / EMA requirements.

A Sponsor representative will medically review all SAE reports.

A Sponsor representative will forward SAE, ECI and pregnancy reports within one working day to MSD.

Every SAE, being assessed by either the investigator or the sponsor as suspected to be related to IMP und assessed as being either unexpected or unexpected with regard to outcome or severity of the event will be reported by the sponsor as SUSAR to the competent authority, responsible ethics committee and investigators of the trial in line with the national regulations in effect (German drug law [AMG] and GCP-V § 13).

Fatal or life-threatening SUSARs must be reported as soon as possible, but no later than 7 days; further important information to these cases may be reported as followup within additional 8 days. All others SUSARs have to be reported no later than 15

days.

Also all adverse events which can change the benefit-risk ratio of the study drugs or otherwise fulfill the criteria outlined in GCP-V §13 Abs.4 have to be handled/reported as SUSARs.

7.6 Handling of Safety Parameters

7.6.1 Adverse events

Adverse events can be spontaneously reported or elicited during open-ended questioning, examination, or evaluation of a subject. (In order to prevent reporting bias, subjects should not be questioned regarding the specific occurrence of one or more AEs.)

Medically significant adverse events regardless of causality will be followed until resolved or considered stable. All subjects with serious adverse events must be followed up for outcome.

It will be left to the investigator's clinical judgment to determine whether an adverse event is related and of sufficient severity to require the subject's removal from treatment or from the study. A subject may also voluntarily withdraw from treatment due to what he or she perceives as an intolerable adverse event. If either of these situations arises, the subject should be strongly encouraged to undergo an end-oftreatment assessment and be under medical supervision until symptoms cease or the condition becomes stable.

7.6.2 Overdose of pembrolizumab

No specific information is available on the treatment of overdose of pembrolizumab. In the event of overdose, pembrolizumab should be discontinued and the subject should be observed closely for signs of toxicity. Appropriate supportive treatment should be provided if clinically indicated. If an adverse event(s) is associated with ("results from") the overdose of pembrolizumab, the adverse event(s) is reported as a serious adverse event, even if no other seriousness criteria are met.

7.6.3 Treatment and Follow-up of Adverse Events

Adverse events, especially those for which the relationship to test drug is not "unrelated", should be followed up until they have returned to baseline status or stabilized. If a clear explanation is established it should be recorded on the eCRF. All subjects with serious adverse events must be followed up for outcome.

7.6.4 Treatment and Follow-up of Events of Clinical Interest

See section 6.3.2

7.6.5 Follow-up of Abnormal Laboratory Test Values

In the event of unexplained abnormal laboratory test values, the tests should be repeated immediately and followed up until they have returned to the normal range and / or an adequate explanation of the abnormality is found. If a clear explanation is established it should be recorded in the eCRF.

7.6.6 Contraception and Pregnancy

Pembrolizumab may have adverse effects on a fetus in utero. Furthermore, it is not known if pembrolizumab has transient adverse effects on the composition of sperm. For this trial, male subjects will be considered to be of non-reproductive potential if they have azoospermia (whether due to having had a vasectomy or due to an underlying medical condition).

Female subjects will be considered of non-reproductive potential if they are either:

(1) postmenopausal (defined as at least 12 months with no menses without an alternative medical cause; in women < 45 years of age a high follicle stimulating hormone (FSH) level in the postmenopausal range may be used to confirm a post-menopausal state in women not using hormonal contraception or hormonal replacement therapy. In the absence of 12 months of amenorrhea, a single FSH measurement is insufficient.);

OR

(2) have had a hysterectomy and/or bilateral oophorectomy, bilateral salpingectomy or bilateral tubal ligation/occlusion, at least 6 weeks prior to screening;

OR

(3) has a congenital or acquired condition that prevents childbearing.

Female and male subjects of reproductive potential must agree to avoid becoming pregnant or impregnating a partner, respectively, while receiving study drug and for 120 days after the last dose of study drug by complying with one of the following:

(1) practice abstinence[†] from heterosexual activity;

OR

(2) use (or have their partner use) acceptable contraception during heterosexual activity.

Acceptable methods of contraception are[‡]:

Single method (one of the following is acceptable):

- intrauterine device (IUD)
- vasectomy of a female subject's male partner
- contraceptive rod implanted into the skin

Combination method (requires use of two of the following):

- diaphragm with spermicide (cannot be used in conjunction with cervical cap/spermicide)
- cervical cap with spermicide (nulliparous women only)
- contraceptive sponge (nulliparous women only)
- male condom or female condom (cannot be used together)

 hormonal contraceptive: oral contraceptive pill (estrogen/progestin pill or progestin-only pill), contraceptive skin patch, vaginal contraceptive ring, or subcutaneous contraceptive injection

†Abstinence (relative to heterosexual activity) can be used as the sole method of contraception if it is consistently employed as the subject's preferred and usual lifestyle and if considered acceptable by local regulatory agencies and ERCs/IRBs. Periodic abstinence (e.g., calendar, ovulation, sympto-thermal, post-ovulation methods, etc.) and withdrawal are not acceptable methods of contraception.

‡If a contraceptive method listed above is restricted by local regulations/guidelines, then it does not qualify as an acceptable method of contraception for subjects participating at sites in this country/region.

Subjects should be informed that taking the study medication may involve unknown risks to the fetus (unborn baby) if pregnancy were to occur during the study. In order to participate in the study subjects of childbearing potential must adhere to the contraception requirement (described above) from the day of study medication initiation (or 14 days prior to the initiation of study medication for oral contraception) throughout the study period up to 120 days after the last dose of trial therapy. If there is any question that a subject of childbearing potential will not reliably comply with the requirements for contraception, that subject should not be entered into the study.

A female patient must be instructed to immediately inform the investigator if she becomes pregnant during the study. The study treatment must immediately be stopped and the patient must be withdrawn from the study. The investigator should counsel the patient; discuss the risks of continuing the pregnancy, and possible effects on the fetus. Monitoring of the patient should continue until conclusion of the pregnancy.

